Life Goals (LG) description and operationalization: The evidence for Life Goals was described earlier. There are three stages to the Life Goals program: initial contact, group sessions, and follow-up contacts/referral (Table 2). First, upon creating a list of patients appropriate for LG, providers will review medical records and confirm eligibility (see above). The LG provider will make an initial call to the patient, and introduce the LG program and schedule group sessions. After the LG provider identifies 6-10 patients, he or she will initiate the first group session, and will hold cohorts of group sessions until enrolling 20 participants. Participants can make up sessions over the phone or in person if they are unable to make group sessions. In the sessions, the LG provider will encourage active discussions that progressively have participants identify triggers to the symptom or episode, develop an action plan for identifying warning signs of symptoms, and an activity plan for adopting a specific health behavior to mitigate symptoms and promote wellness. Participants will be given a workbook with exercises on behavior change goals, symptom assessments, and coping strategies. The LG provider will then contact the patient six times after the end of the group sessions on a weekly basis to review symptoms, behavior change, and any concerns the patient might have. LG providers will also track patients' mood symptoms and health behaviors using a registry. Once participants complete the LG program, a one-page summary of their current mood symptoms and health behavior changes will be routed to their primary care or mental health provider for treatment planning. As in previous studies, LG providers will be trained to inform providers immediately if patients have elevated symptoms or suicidal ideation. This is incorporated into the clinic's routine clinical care. Study staff (outside outcomes assessors) will complete outcomes assessments on up to 20 patients who are receiving Life Goals at the clinic in order to measure the program's reach over time.

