LG fidelity: Because this study is designed to assess real-world implementation of routine clinical care, minimally invasive measures developed by study investigators will be used to assess use of LG services. LG providers will complete a computerized log of LG encounters, which will

ascertain the number of completed group sessions and provider follow-up contacts received by each patient. LG fidelity will also be assessed using a previously established measure that combines information from the LG provider logs with confirmatory information from patient surveys. The fidelity monitor calculates a total score based on number of group sessions (0-4) and follow-up contacts (0-6) completed by each patient. Average patient completion of group sessions of $\geq 75\%$ was associated with improved mental health-related quality of life.

Table 4: Recording Time Spent on REP, Facilitation, and LG

REP (all sites)
LG provider and site representative time spent at in-service, training
LG provider time spent with LG trainer on phone follow-ups, documentation
Project staff (investigators, personnel): Packaging LG, training, site contacts, note-taking
EF (REP+EF sites)
LG provider time spent with External Facilitators (phone contacts, email follow-ups)
LG provider actions taken to facilitate LG, documentation
Project staff (EF): Time spent with provider contacts, follow-up technical assistance, documentation of goals with each site
IF (REP+EF/IF sites)
Time IF spent with EF, LG providers in meetings and establishing goals, site priorities, develop rapport
Time IF spent working out LG barriers, strategizing and aligning LG goals with site goals
Time IF spends with EF and LG provider in summarizing implementation progress with leadership, business plan development
LG Implementation (all sites)
Group sessions: Number of outpatient clinic visits w/ LG patients actually completed
Follow-up contacts: Time spent on each contact
Other Face-Time: Any time spent seeing LG patients face-to-face or on phone outside of sessions/contacts
Phone Time: Any time spent on the phone only with LG patients. Include time spent leaving messages, playing "phone tag", etc.
Care Coordination: Any and all time spent on behalf of a LG patient when patient is not present (e.g., phone, consultation)
Charting Time: Any time spent charting for a LG patient (e.g., registry, progress notes, updating treatment plans, etc.)

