Intent-to-treat. Every effort will be made to collect patient level outcomes across all 80 sites and patients (N=1600) to conduct the primary and exploratory analyses (see below). The 40 sites randomized at month 6 (total 800 patients) will be included in the intent-to-treat randomized sample. The Primary Aim analysis will compare strategies in non-responding sites (k=40) beginning with **REP+EF/IF** versus strategies beginning with **REP+EF** on longitudinal change in patient-level SF-12 mental health scores (MCS- primary outcome). This analysis is a comparison of cells A+B+C vs. D+E (Figure 2). For this analysis, the longitudinal outcome is SF-12 mental health scores measured at Months 6 (pre-randomization), 12, 18, and 24. The primary contrast is the between groups difference in change from Month 6 to Month 18. The follow-up contrast at Month 24 will also be examined in this and all subsequent analyses. Linear mixed models (LMM), also known as random effects models, fit with SAS PROC MIXED will be used to analyze the longitudinal data. LMMs use all available measurements, allowing subjects to have an unequal number of longitudinal observations and producing unbiased parameter estimates as long as unobserved values are missing at random. The analysis will fit a 3-level (repeated measures for each person clustered within site) LMM with fixed effects for the intercept, time, group, and a group-by-time interaction term, where group is an indicator of **REP+EF/IF** vs. **REP+EF**. The LMM will also include random effects for site and time, an unstructured within-person correlation structure for the residual errors, and it will adjust for the following pre-randomization measures collected through Month 6: state and type of practice (primary care- or mental health site). Model diagnostics will be used to determine the suitability of more parsimonious (e.g., autoregressive) correlation structures, and nonlinear (e.g., piecewise linear or quadratic) effects for time. LMMs similar to the above for the primary outcome will be conducted for the secondary outcomes: **REP+EF/IF** vs. **REP+EF** on change in number of LG encounters, functional impairment, and psychiatric symptoms.

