The goal of the Secondary Aim 1 analysis is to determine whether continuing **REP+EF** versus augmenting with **REP+EF/IF** leads to changes in outcomes, among sites who are non-responsive at Month 12. This analysis is a comparison of cells B vs. C (Figure 2). Both primary and secondary longitudinal outcomes above will be examined using an LMM similar to that described above, except (a) including only the subset of sites that do not respond at Month 12 to **REP+EF**, (b) using monthly longitudinal outcomes from Month 12 to Month 24, and (c) the LMM will use dummy-indicators for time (i.e., time-saturated model since there are only 3 measurement times for each longitudinal outcome).

The Secondary Aim 2 analysis will involve an analysis of implementation costs. The implementation (REP, EF, IF) costs will be summed for each site as a measure of total costs and changes in costs will also be assessed over time (6, 12, 18, 24 months). An exploratory analysis of the incremental effectiveness of IF by comparing costs from sites given **REP+EF/IF** versus those with **REP+EF** will be conducted from the site's perspective. In regression models of costs, Generalized Linear Models with log link functions will be used to correct for heteroscedasticity and reduce the impact of outliers. Effectiveness will be measured by changes in health utilities using the SF-6 (a subset of SF-12 questions) as well as the Euro-QOL 5D. Cost-effectiveness will be calculated as the ratio of incremental average site-level cost and incremental average effectiveness (change in patient-level utilities) of IF. A standard nonparametric bootstrapping approach will be used to calculate confidence intervals and cost-effectiveness acceptability curves.

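### LG uptake is analysed as change in encounters without saying whether the count is per interval or cumulative; one reading can reverse the comparison and the other is distorted by linear time

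*Combined protocol and SAP*

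**What the plan says.** Section VI (Intent-to-treat paragraph) sets out the SF-12 analysis. The outcome is "measured at Months 6 (pre-randomization), 12, 18, and 24", and "The primary contrast is the between groups difference in change from Month 6 to Month 18". The fixed effects are intercept, time, group and group-by-time; nonlinear time enters only if model diagnostics call for it. The section then states that "LMMs similar to the above for the primary outcome will be conducted for the secondary outcomes", and lists these as "change in number of LG encounters, functional impairment, and psychiatric symptoms". It gives no separate contrast, counting rule or time window for encounters.

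Table 3 describes uptake only as numbers of sessions and contacts. In section V.F (LG fidelity), the monitor "calculates a total score based on number of group sessions (0-4) and follow-up contacts (0-6) completed by each patient". Section V.E describes a single pass through the programme: group sessions (weekly, according to section III), after which "The LG provider will then contact the patient six times after the end of the group sessions on a weekly basis", then completion and a summary sent to the treating provider. No repeat course is described.

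For Secondary Aim 1, section VI calls for dummy indicators for time, listed as a departure from the main model, and for "using monthly longitudinal outcomes from Month 12 to Month 24". The same sentence says there are only three measurement times.

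**The concern.** A quality-of-life score is a state, and its change between two visits has a plain meaning. Encounters are a quota that is used up. A patient who completes LG in Months 7-12 has none left to receive in Months 13-18. If the value at each visit covers only the preceding interval, early delivery produces a low Month 18 value and therefore a poor change score.

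Use of LG is named ahead of the clinical measures in the Primary Study Aim, and it is the route by which facilitation is meant to help patients. An uptake result with the wrong sign, or much reduced in size, would mislead on whether adding an Internal Facilitator increases use of the programme.

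**Working it through.** The plan gives no figure for the uptake contrast, so there is none to reproduce. The check applies the written contrast to mean delivery profiles.

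**Inputs from the documents**
- Maximum per patient: 4 sessions + 6 contacts = 10.
- Course length: 4 weekly sessions, then 6 weekly contacts, about 10 weeks. It fits inside one six-month interval.
- Cohort: 20 patients per site (section V.C).
- Measurement times: Months 6, 12, 18 and 24.

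**Assumed inputs** (the documents give none)
- Patients completing all 10 encounters in Months 0-6, 7-12 and 13-18: REP+EF/IF site 4, 12, 2; REP+EF site 4, 3, 7. No delivery after Month 18.
- Both sites are under 10 patients at Month 6, which fits the patient-count part of the non-response rule in section V.C.

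Mean encounters per patient in an interval = completers × 10 / 20.

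| | Month 6 | Month 12 | Month 18 | Month 24 |
|---|---|---|---|---|
| EF/IF, per interval | 2.0 | 6.0 | 1.0 | 0 |
| EF, per interval | 2.0 | 1.5 | 3.5 | 0 |
| EF/IF, cumulative | 2.0 | 8.0 | 9.0 | 9.0 |
| EF, cumulative | 2.0 | 3.5 | 7.0 | 7.0 |

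**Target.** Encounters delivered from Month 6 to Month 18: EF/IF 6.0 + 1.0 = 7.0; EF 1.5 + 3.5 = 5.0. The true difference is +2.0 in favour of EF/IF.

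**Per-interval count, time-specific means.** EF/IF 1.0 - 2.0 = -1.0; EF 3.5 - 2.0 = +1.5. The difference is -2.5, so the sign is reversed.

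**Cumulative count, time-specific means.** EF/IF 9.0 - 2.0 = 7.0; EF 7.0 - 2.0 = 5.0. The difference is +2.0, which is correct.

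**Linear time.** Months 6, 12, 18 and 24 are coded 0, 1, 2, 3. With independent errors, slope = (-1.5y₀ - 0.5y₁ + 0.5y₂ + 1.5y₃)/5, and the Month 6-to-18 change is 2 × slope.
- Cumulative, EF/IF: (-3 - 4 + 4.5 + 13.5)/5 = 2.2, change 4.4.
- Cumulative, EF: (-3 - 1.75 + 3.5 + 10.5)/5 = 1.85, change 3.7. Difference **+0.7** against a true +2.0.
- Per interval, EF/IF: (-3 - 3 + 0.5 + 0)/5 = -1.1, change -2.2.
- Per interval, EF: (-3 - 0.75 + 1.75 + 0)/5 = -0.4, change -0.8. Difference -1.4, still reversed.

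Refitting the same profiles by generalised least squares with first-order autoregressive errors (correlation 0.8) gives +1.3 for the cumulative count, still short of +2.0, and -0.08 for the per-interval count.

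**Other assumed profiles**
- *Faster arm also delivers more.* Assumed coverage is 60% then 15% in the faster arm, against 30% then 30%, with no delivery before Month 6. Totals by Month 18 are 7.5 v 6.0, a true difference of +1.5. Per interval with time-specific means: 1.5 - 3.0 = -1.5. Cumulative with time-specific means: +1.5. Cumulative with linear time: +0.6 (independent errors) to +0.98 (autoregressive, 0.8).
- *Equal totals.* Everyone gets 10 encounters, in Months 6-12 in one arm and 12-18 in the other. The true difference at Month 18 is 0. Per interval with time-specific means: -10. Cumulative with time-specific means: 0. Cumulative with linear time: 6.0 - 8.0 = -2.0 (independent errors), shrinking to -0.12 (autoregressive, 0.8).

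**The case against.** The strongest reply is that nothing in the documents says encounters are counted per interval. The fidelity score in section V.F is a total per patient, which reads naturally as a running count. On that reading, with time-specific means, the planned change contrast gives +2.0, exactly the encounters delivered since randomisation. This stands: the reversal is conditional on a per-interval count. But the score carries no time window, so the text does not settle the matter. Nor does a cumulative count alone repair the analysis, because categorical time is specified only for Secondary Aim 1. Diagnostics might lead to piecewise or quadratic time in the main model, but that is not a commitment.

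Applying the Month 6-to-18 contrast to uptake is itself an inference from the statement that the models are similar and from the word change. It is the natural reading, since no other uptake contrast is given. Month 18 is also not the only view: "The follow-up contrast at Month 24 will also be examined in this and all subsequent analyses", and Month 12 values would show faster delivery. That helps interpretation but does not define the endpoint.

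A reader might infer that the Month 12 re-randomisation is a further error because it raises REP+EF uptake in Months 12-18. The documents do not support that. Section VI compares strategies beginning with each option (cells A+B+C against D+E), so later augmentation belongs to the comparison. Only about half of the non-responsive REP+EF sites would receive it. It makes late delivery in that arm plausible and does no more.

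The monthly wording for Secondary Aim 1 conflicts with three measurement times. That is a separate inconsistency and not evidence of a per-interval count.

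**Conclusion.** The point holds as a definition gap with consequences. The plan fixes neither the counting window nor the form of time for uptake, and of the combinations it permits, only a cumulative count with time-specific means is sound. In the main illustration, a per-interval count gives -2.5 against a true +2.0. A cumulative count with linear time gives +0.7 with independent errors and no delivery after Month 18; stronger serial correlation narrows the shortfall without removing it. With a cumulative count, the direction was right in the profiles where the faster arm delivered more. With equal totals, linear time placed the faster arm lower.

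A reader might infer that the planned analysis will rank the faster strategy as worse. That goes too far: the delivery profiles are assumed, they show what the wording permits and not what is likely, and the reversal disappears under one permitted reading. The outcome is secondary in Table 3, so the SF-12 primary analysis is unaffected. Because LG use is named in the Primary Aim and the remedy is nearly free, the wording should be changed.

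**What to change.** Define uptake as cumulative encounters per pre-identified cohort patient from the Month 6 randomisation to Month 18, then to Month 24, scored 0-10, with sessions (0-4) and contacts (0-6) also shown. Compare arms at those fixed times, using either one value per patient or categorical time in the mixed model, with encounters before Month 6 as a covariate and allowance for site clustering. The mixed model need not be dropped. For Secondary Aim 1, count cumulatively from Month 12 to Month 24. Leave the Month 12 augmentation within the strategy comparison.

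The cost is SAP wording and a model that differs slightly from those for the other secondary outcomes. One check is needed first. Section V.F says the provider logs give numbers of sessions and contacts per patient but does not mention dates. Logs and reporting sheets are completed monthly (Table 1 and the fidelity paragraph of section V.E), so assigning encounters to these windows should be feasible, but it must be confirmed.

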
The overarching goal of this study is to build the most cost-effective adaptive implementation strategy involving REP and Facilitation to enhance the update of an EBP for mood disorder and subsequent changes in patient outcomes using clinical assessments available in routine care. The EBP, Life Goals (LG), is an evidence-based psychosocial treatment shown to improve outcomes among patients with mood disorders and will be implemented as part of routine clinical care at each organization. In this study, sites initially receiving REP that have not fully implemented LG (e.g., <10 patients receive the LG EBP) will be randomized to receive additional External Facilitation (**REP+EF**) or External plus Internal Facilitation (**REP+EF/IF**). At 12 months, sites that are non-responsive to External Facilitation (**REP+EF**) will be re-randomized to receive **REP+EF** or **REP+EF/IF** and then followed for another 12 months to determine whether longer-term exposure to Facilitation is needed. Because sites and not patients will be randomized, the EBP (LG) is already an established evidence-based clinical practice that will be implemented as part of routine clinical care, and because all sites will receive some additional state-of-the-art

implementation support through Facilitation, this project involves health care operations improvement within select healthcare systems.

Primary Study Aim. To determine whether sites that do not exhibit response to REP alone after 6 months (e.g., <10 patients receiving LG), the effect of adding an External and Internal Facilitator (**REP+EF/IF**) versus adding an External Facilitator alone (**REP+EF**) on use of the EBP (LG) and changes in routinely collected patient clinical assessments (health-related related quality of life and mood symptoms).

Secondary Aim 2. To estimate the costs of REP+EF/IF compared to REP+EF at the sites.

Secondary Aim 3. To describe the implementation of EF and EF/IF, including interaction between the two roles and the specific strategies EFs and IFs use to facilitate LG uptake across different sites.

Results from the project will be used to inform activities designed to implement promising ways to improve clinical care and healthcare operations.

III. Background and Significance

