F. Data Collection and Measures

Data for primary and secondary aims will be collected by study staff from patient surveys, organizational surveys, and provider logs. The assessment package previously developed and implemented by study investigators (R34 MH74509, R01 MH79994) was informed by the RE-AIM framework for evaluating implementation of EBPs. Key measures include patient-level outcomes, LG uptake and fidelity, organizational factors, and REP, EF, and IF activities (Table 3). Data sources include patient-level (surveys), site-level (provider surveys), and project staff logs.

Patient data: Lists of patients and contact information that were identified by the LG providers during the first 3 months of REP (pre-randomization) will be sent to study outcomes assessors who will conduct phone surveys at baseline (after the REP provider training is complete), and 6, 12, 18, and 24 months later. Patient baseline assessments will include assessments already used

in routine clinical care and will be conducted by project staff by phone after the LG provider identifies eligible patients but before the first LG sessions are implemented. Once project staff receive patient lists, they will contact patients, describe the purpose of the study, and ask if the patients would like to participate. Patients will be compensated \$10 for completing each assessment. Patient-level data will be coded with a unique identifier. There will be a crosswalk file that is password protected that is only available to be accessed by study staff that will link unique study ID with a link to the person's identity.

Table 3: Primary and Secondary Assessments – Baseline and Follow-ups

Aims	Measure	Source
1a. Primary outcomes	Health-related quality of life-SF-12 mental health score	Patient survey
1b. Secondary outcomes	Functional impairment-WHO-DAS	Patient survey
	Psychiatric symptoms-PHQ-9, GAD-7, ISS	Patient survey
	LG fidelity and uptake (# sessions, contacts)	LG provider logs, patient surveys
Secondary aims	LG implementation costs (patient, site perspective)	Patient survey, chart review, logs
	REP costs	Study staff logs
	Facilitation costs	Staff, LG provider, Facilitator logs
Covariates	Patient demographic, clinical factors, behaviors use	Patient survey, chart review, logs
	Organizational factors (OTM, ORCA, EBPAS)	Site leader, provider surveys

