Implementation Strategy (REP, EF/IF) Use and Costs (Table 4): Personnel time is likely to account for the vast majority of costs associated with REP and Facilitation. All activities involving REP, EF, and IF will be documented using previously established log forms (e.g., R01 MH 79994) and all costs will be multiplied by personnel wage rates including fringe. We will estimate time costs incurred by both site employees as well as project staff (REP trainer, Facilitators). We chose to focus on a cost analysis from the perspective of the sites because the added cost of paying for and providing Internal Facilitation will be the major concern of these stakeholders, who are the target audience for potentially spreading value-based implementation frameworks

REP Costs from the site's perspective: We will estimate the costs of the REP implementation from the site's perspective by collecting information on the total time LG providers spent on 1) in-services, 2) training, and 3) monitoring by surveying the providers involved in each step based on the LG registry log.

REP and External Facilitation costs: Total costs of REP and EF implementation will be estimated based on study staff logs by summing up the total time spent by the study staff in LG package dissemination, in-services, training, and follow-up site calls and documentation.

Internal Facilitation Costs: IF costs are primarily borne by the site and are detailed in Table 4. Each IF will complete a log of activities using similar procedures in ROCC. The total time spent in IF activities will be multiplied by personnel wage rates.

LG Costs from the site's perspective will also be estimated for each site. Study staff will ascertain information from the LG provider registry on number and time for each group session, follow-up contact, as well as for additional provider and patient encounters and clinical documentation

(Table 4).

VI. Analyses and Evaluation

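### The cost-effectiveness ratio has no stated place for the sites' cost of delivering Life Goals; read naturally it omits that cost, which favours IF if IF raises LG delivery

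*Combined protocol and SAP*

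**What the plan says.** In section VI, the Secondary Aim 2 paragraph starts with implementation costs: "The implementation (REP, EF, IF) costs will be summed for each site as a measure of total costs". It then sets out an exploratory comparison of REP+EF/IF with REP+EF sites, which "will be conducted from the site's perspective". On the benefit side, "Effectiveness will be measured by changes in health utilities using the SF-6", together with the Euro-QOL 5D. The ratio follows: "Cost-effectiveness will be calculated as the ratio of incremental average site-level cost and incremental average effectiveness (change in patient-level utilities) of IF". Bootstrap intervals and acceptability curves are built on it.

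LG delivery cost is dealt with elsewhere. Section V.F, under Implementation Strategy Use and Costs, says: "LG Costs from the site's perspective will also be estimated for each site". Table 4 gives LG its own block, apart from the REP, EF and IF blocks, covering sessions, follow-up contacts, other face and phone time, care coordination and charting. Table 3 lists under the secondary aims a row that begins "LG implementation costs (patient, site perspective". Section VI does not say where any of this enters the analysis.

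The overarching goal in section II is to "build the most cost-effective adaptive implementation strategy involving REP and Facilitation".

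**The concern.** The numerator and the denominator of the ratio may not cover the same thing. The IF's task is to raise LG uptake (section V.E), and the number of LG encounters is compared between arms as a secondary outcome (section VI). The plan therefore allows for, and hopes for, a difference in LG volume. Patient benefit would be expected to come largely through LG, which the sites' own staff deliver. If the ratio counts the utility gain but not the staff time spent delivering the extra LG, incremental cost is understated, and by more the better IF works. Sites are the stated audience for the cost results, and a site that takes up IF pays for the facilitator and for any extra LG.

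**Working it through.** The documents state no cost-effectiveness ratio, threshold, wage rate or expected difference in LG volume, so there is no planned figure to reproduce. The $5,500 IF cost is given without hours or wages and cannot be rebuilt.

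**Form of the bias.** Let dC_impl, dC_LG and dU be the differences between REP+EF/IF and REP+EF in implementation cost, LG delivery cost and utility change.

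- Ratio on the natural reading: dC_impl / dU
- Ratio with LG delivery: (dC_impl + dC_LG) / dU
- Second over first: 1 + dC_LG / dC_impl

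The factor does not depend on dU. It exceeds 1 when dC_impl and dC_LG are positive, and equals 1 when dC_LG = 0. Reading it as an understated cost per unit of benefit also needs dU > 0.

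**Inputs from the documents.**

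- Four group sessions of 60-80 min and six contacts of 15-20 min (Table 2). Section III gives two-hour sessions instead.
- Groups start once 6-10 patients are identified (section V.E).
- 20 LG patients expected per site (section V.E).
- IF cost of $5,500 per site over 12 months in the earlier trial (section IV).

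**Assumed, not in the documents.** 5-10 extra LG patients per REP+EF/IF site; $40-$60 per provider hour with fringe; REP and EF costs equal between arms, so that dC_impl = $5,500.

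**Provider hours per patient** = (4 x session minutes / group size + 6 x contact minutes) / 60

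- Low: (4 x 60 / 10 + 6 x 15) / 60 = (24 + 90) / 60 = 1.9 h
- High, Table 2: (4 x 80 / 6 + 6 x 20) / 60 = (53.3 + 120) / 60 = 2.9 h
- High, two-hour sessions: (4 x 120 / 6 + 6 x 20) / 60 = (80 + 120) / 60 = 3.3 h

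**Omitted cost per site** = extra patients x hours x hourly cost

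- Low: 5 x 1.9 x $40 = $380; $380 / $5,500 = 6.9%
- High: 10 x 2.9 x $60 = $1,740; $1,740 / $5,500 = 31.6%

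The factor is therefore about 1.07 to 1.32.

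**Sensitivity to the assumptions.**

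| Case | LG cost per site | Factor |
|---|---|---|
| No extra LG | $0 | 1.00 |
| 5 extra, $25/h, 1.9 h | $238 | 1.04 |
| 10 extra, $40/h, 1.9 h | $760 | 1.14 |
| 10 extra, $40/h, 3.33 h | $1,333 | 1.24 |
| 20 extra, $60/h, 3.33 h | $4,000 | 1.73 |

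If extra patients only fill existing groups, session time adds nothing and the hours are the contacts alone, 1.5 to 2.0 h. Then 5 x 1.5 x $40 = $300 (5.5%) and 10 x 2.0 x $60 = $1,200 (21.8%). In the other direction, none of these figures includes the phone, coordination and charting time that Table 4 logs. If that time equalled the direct time (assumed), the main range would double to $760-$3,480, or 14% to 63% of $5,500.

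**The case against.** **The numerator is not expressly the REP, EF and IF sum.** That sum belongs to the implementation-cost analysis, and the ratio uses a different term, site-level cost. REP and EF costs in section V.F include study-staff time that the site does not pay, so the sum is not clearly a site-perspective cost. LG is costed from the site's perspective, and Table 3 labels it an implementation cost. The authors may have meant to include it. This stands: a reader might infer that the plan expressly excludes LG, and it does not. But the paragraph offers no other definition of cost, so the ambiguity must be settled before analysis.

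**The direction is conditional.** A reader might infer that IF will look cheaper than it is. The only evidence of more LG is the earlier trial's comparison of REP+EF/IF with REP alone (section IV), not with REP+EF. The same section says that the value of IF added to EF has not been tested in a fully powered trial. Non-responding REP+EF sites may also receive IF from Month 12, which could narrow the difference in LG volume. Nor do the documents say that LG is the only route to a utility gain. All of this stands.

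**Gross LG cost may be too high.** The LG package includes billing codes (section V.E), so sites may recover part of the cost. No revenue offset is planned. This limits how the corrected ratio should be read, but does not justify leaving LG cost out.

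**The size rests on assumptions.** Wages and extra patients are not in the documents. The $5,500 covers 12 months, whereas section V.E describes a six-month IF period here. This stands, and the percentages are illustrative.

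**Scope.** Secondary Aim 2 is to estimate the costs of the two strategies at the sites, and implementation-only cost is a reasonable answer to that. It is less suitable as the numerator of a ratio whose denominator is patient benefit.

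**Conclusion.** The concern holds as a gap in the definition of the cost-effectiveness numerator. Read naturally, the ratio omits LG delivery cost, although that cost is collected per site from the site's perspective. If REP+EF/IF raises LG delivery over REP+EF and utilities improve, incremental cost and the ratio are understated, and the ratio with LG included is 1 + dC_LG / dC_impl times the planned one. If LG volume does not differ, there is no bias.

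The documents cannot give the size. Under the main assumptions (5-10 extra patients per site, $40-$60 per hour, Table 2 session lengths, dC_impl of $5,500), the omitted cost is roughly $380 to $1,740 per site, or 7% to 32% of the earlier IF cost. These figures are not an estimate for this trial, and the documents do not support a claim of demonstrated bias in favour of IF. The ratio is exploratory and the primary SF-12 comparison is unaffected, but cost-effectiveness is part of the overarching goal, so the definition should be corrected before analysis.

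**What to change.** In the Secondary Aim 2 paragraph of section VI:

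1. Define the numerator of the cost-effectiveness ratio as site-borne REP + EF + IF + LG delivery cost, with LG cost taken from the Table 4 log. Use the same total in the bootstrap intervals and acceptability curves.
2. Keep the implementation-only sum as the Secondary Aim 2 cost result, and report the ratio on that basis as a sensitivity analysis.
3. State that LG cost is gross of any billing revenue unless such revenue is recorded.

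This is a change of wording only, because the LG time data are already to be collected and costed. The downsides are that the ratio for IF may become somewhat less favourable, and that gross LG cost may overstate the net cost to sites that bill for sessions. Reporting both ratios shows how much the inclusion of LG matters.
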